9.6.2 Demographics

At Visit 1 each patient shall be required to provide basic demographic information including date of birth, gender, ethnicity and race.

9.6.3 Medical History

At Visit 1 patients will be questioned about medical history, including acute and chronic medical history and medical history relevant to their vaginal atrophy, as well as all concomitant medication use within the previous 6 months. At Visit 2 medical history will be reviewed and updated if changes have occurred.

9.6.4 Vital Signs

The patient's vital signs will be recorded (pulse, blood pressure, temperature and respiration rate) at Visits 1, 2 and 3. At Screening and Randomization blood pressure reading cannot exceed 150/90 to qualify for randomization.

9.6.5 Physical Exam, Pelvic Exam and Breast Exam

At Visit 1 the Investigator will perform a general physical exam including pelvic exam and breast exam. The results of this exam should, in the Investigator's opinion, be consistent with a diagnosis of estradiol-deficient vaginal/vulvar atrophy for the patient to be eligible for inclusion in the study. Additionally this exam should exclude the possibility that the symptoms could be caused by any concurrent disease (e.g., bacterial vaginosis, candida infection). Any patient diagnosed with, or with any suspected concurrent vaginal infection or other vaginal disease will be excluded from the study.

At Visit 3 the Investigator will perform a general physical exam including pelvic and breast exams, any negative findings on exam should be reported as Adverse Events.

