9.7 Adverse Events

The patients will be monitored throughout the study for any adverse experiences. AEs will be collected through both solicited and unsolicited means and subsequently coded in tabular form using the MedDRA Version 17.0 or higher adverse event dictionary. The patients will be encouraged to report signs, symptoms, and any changes in health to the clinic staff. Severity of each AE will be determined by the clinic staff based on observation and questioning of the patient. The Investigator will judge the relationship of the event to the study treatments.

Definitions

An adverse event is any untoward medical occurrence in a clinical investigational patient administered a pharmaceutical product, regardless of whether it has a causal relationship with this treatment. In this study, any adverse event occurring after the patient has signed the informed consent form should be recorded and reported as an adverse event.

An adverse event can, therefore, be any unfavorable and unintended physical sign, symptom, or laboratory parameter that develops or worsens in severity during the course of the study, or significant worsening of the disease under study or of any concurrent disease, whether or not considered related to the study drug. A new condition or the worsening of a pre-existing condition will be considered an adverse event. Stable chronic conditions (such as arthritis) that are present before study entry and do not worsen during the study will not be considered adverse events.

Abnormal results of diagnostic procedures, including laboratory findings, are considered to be AEs if the abnormality:

- results in study withdrawal
- is associated with a serious adverse event (SAE)
- is associated with clinical signs or symptoms
- is considered by the physician to be of clinical significance

CONFIDENTIAL PROTOCOL

A Randomized, Double-Blind, Placebo-Controlled, Parallel Design, Multiple-Site Study to Evaluate the Therapeutic Equivalence of Estradiol Vaginal Cream USP, 0.01% (Teva Pharmaceuticals, USA) to Estrace® Estradiol Vaginal Cream, USP, 0.01% (Warner Chilcott) in the Treatment of Atrophic Vaginitis

This includes events not seen at baseline, or worsened if present at baseline.

Recording and Reporting Adverse Events

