10.8 Safety Analysis

All study patients who use at least one application of the study drugs will be included in the safety analysis. Adverse events will be classified using standard MedDRA terminology Version 17.0 or higher and summarized by treatment group. Summary tables comparing the type, incidence, severity and Investigator's opinion to drug relationship relation will be prepared by treatment group. Signs and symptoms of atrophic vaginitis will not be considered adverse events, unless in the Investigator's opinion, they have increased in frequency and/or severity to such an extent that the Investigator/patient considers that it is in the patient's best interest to be dropped from continued participation in the study and given alternative therapy for their condition. If sufficient data exist, adverse event frequencies will be compared between treatments using Fisher's exact test or a similar test. Concomitant medication use during the study will be tabulated by patient. Adverse events reported during the study will be tabulated in a summary table listing the type, incidence, severity and Investigator's opinion to drug relationship.

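### The Visit 3 exam rule reports findings as adverse events without comparison to Visit 1 or an exception for the study disease, contradicting the protocol's own adverse event rules

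*Protocol*

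**What the plan says.** **The exam rule.** Protocol 9.6.5 has the Investigator repeat the general physical exam, with pelvic and breast exams, at Visit 3, and adds that "any negative findings on exam should be reported as Adverse Events". SAP 8.1.5 carries the same sentence for the general and pelvic exam. Neither place refers to Visit 1, to section 9.7, or to the disease under study.

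**The entry condition.** The same section requires the Visit 1 exam, in the Investigator's opinion, to "be consistent with a diagnosis of estradiol-deficient vaginal/vulvar atrophy for the patient to be eligible for inclusion in the study".

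**The general definition.** Protocol 9.7 compares with baseline: "A new condition or the worsening of a pre-existing condition will be considered an adverse event". It also says: "Stable chronic conditions (such as arthritis) that are present before study entry and do not worsen during the study will not be considered adverse events". For abnormal results of diagnostic procedures it adds: "This includes events not seen at baseline, or worsened if present at baseline".

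**The disease-specific rules.** Protocol 10.8 and the synopsis both state: "Signs and symptoms of atrophic vaginitis will not be considered adverse events", unless they increase so far that dropping the patient and giving alternative therapy is judged to be in her best interest. Protocol 9.6.6 adds that even worsening need not be recorded as an AE unless additional treatment is required or the Investigator considers it one.

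**The SAP's AE section.** SAP 8.3.1 codes, lists and summarises all reported AEs. It does not repeat the atrophic vaginitis exclusion.

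**The concern.** Every randomized patient should have had an exam consistent with atrophy at Visit 1. If atrophy is still visible at Visit 3 and no worse, 9.6.5 read by itself tells the examiner to report an AE. Sections 9.7 and 10.8 say it is not one. The same holds for any stable abnormality outside the disease, such as a long-standing heart murmur, except that only 9.7 excludes it.

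The two readings would not necessarily affect the arms equally. Under the literal reading the recorded event is failure of the study disease to improve, and that should be less frequent on estradiol if estradiol works. Objective 3 compares safety across Test, Reference and Placebo, and both documents allow AE frequencies to be tested between treatments if the data suffice. Literal reporting could therefore raise the placebo AE rate and make both active creams look relatively safer. If only some sites report this way, AE rates would also differ between sites for reasons unrelated to the drug.

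The word negative is a smaller wording problem, since in clinical use it often means normal. The intended meaning is clear enough, but the sentence should say abnormal.

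**Working it through.** **1. One case set against each rule.** Take a patient with visible atrophy at Visit 1, the same at Visit 3, still in the study, with no additional treatment.

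| Rule | Is it an AE? |
|---|---|
| Protocol 9.6.5 and SAP 8.1.5, Visit 3 sentence | Yes, as written |
| Protocol 9.7, general definition | No: neither new nor worse |
| Protocol 10.8 and synopsis | No: a sign of atrophic vaginitis, exception not met |
| Protocol 9.6.6 | Does not call for it: it addresses worsening, and there is none |
| SAP 8.3.1 | Tabulated if a site has reported it |

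For a stable finding unrelated to atrophy, rows 1 and 2 conflict in the same way and the disease-specific rows do not apply. No passage states an order of precedence.

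**2. Arm sizes.** From 660 randomized at 2:2:1: placebo 660 × 1/5 = 132, which matches the figure in Protocol 7.4; each active arm 660 × 2/5 = 264; both active arms together 528.

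**3. Illustrative size of the effect on an AE comparison.** The documents give no rate of persisting exam-visible atrophy and no rate at which sites would report it. The shares below, of patients given such an AE, are assumptions. Count = arm size × share, with Reference assumed equal to Test. The p-value is the two-sided Fisher's exact test, placebo (132) against Test (264).

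| Assumed share, placebo vs each active arm | Placebo | Test | Test + Reference | Placebo share of events | Fisher p |
|---|---|---|---|---|---|
| 80% vs 40% | 106 | 106 | 212 | 106/318 = 33% | 1.3e-14 |
| 80% vs 60% | 106 | 158 | 316 | 106/422 = 25% | 4.3e-5 |
| 20% vs 10% | 26 | 26 | 52 | 26/78 = 33% | 0.011 |
| 8% vs 4% | 11 | 11 | 22 | 11/33 = 33% | 0.10 |

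The first two rows assume that all visible atrophy is reported. The last two keep the 2:1 rate ratio of the first row and suppose that a quarter or a tenth of it is reported.

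**4. When placebo would hold most of the events.** Let a be the active share and p the placebo share. Placebo supplies more than half only if 132 × p > 528 × a, that is, a < p/4. Even at p = 100% the active share would have to be below 25%. None of the rows above meets this.

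**The case against.** The strongest reply is that 9.6.5 is a procedural paragraph that uses the term Adverse Events, and 9.7 is where the term is defined. On that reading Visit 3 findings are reported only if new or worse, and 10.8 removes atrophic signs in any case. This has force: it is the natural way to read the protocol as a whole, and a careful site would probably follow it. It does not settle the matter. The sentence in 9.6.5 is the specific instruction for the Visit 3 exam, it says any finding, and it does not refer to 9.7. The SAP reproduces it and leaves out the exclusion that would limit it.

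A reader might go further and infer that persisting atrophy becomes an AE throughout the trial. The documents do not support that, because 9.7, 10.8 and the synopsis exclude it; it happens only where a site applies 9.6.5 literally. A reader might also infer that such events would fall mostly on placebo. With 528 active and 132 placebo patients that does not follow, as step 4 shows; only a higher rate per patient is plausible. Nor is a long-standing breast lump a good example, since inclusion criterion 7 requires a normal breast exam at screening, so a lump found at Visit 3 would ordinarily be new.

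Other limits also stand. AE testing is conditional on sufficient data. At the lowest assumed shares the comparison is no longer significant at 5%. Any distortion should fall about equally on Test and Reference. Atrophy entries would be visible by preferred term in table T16.1.9.10.1 and could be checked against Visit 1 in listing L16.2.8.4.

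**Conclusion.** The contradiction is real: unchanged atrophy or another stable exam finding at Visit 3 is an AE under Protocol 9.6.5 and SAP 8.1.5, but not under 9.7, and for atrophy not under 10.8 or the synopsis. The consequence is a risk of inconsistent AE reporting between sites and of bias in the Objective 3 comparison of active with placebo. The direction, a higher rate per patient on placebo, assumes that estradiol visibly improves atrophy by Visit 3 and that some sites follow the literal sentence. The size cannot be derived from the documents; under the assumed shares it ranges from overwhelming to not significant at 5%. The primary equivalence analysis, the superiority analyses, alpha and sample size are unaffected. It should be corrected because the contradiction is plain and the correction costs almost nothing.

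**What to change.** Reconcile the passages as follows.

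- In Protocol 9.6.5 and SAP 8.1.5, replace the sentence with one to this effect: abnormal findings at the Visit 3 exam are compared with Visit 1 and reported as adverse events only if they meet the section 9.7 definition (new or worsened); signs of atrophic vaginitis are handled under sections 9.6.6 and 10.8.
- In SAP 8.3.1, carry over the atrophic vaginitis exclusion from Protocol 10.8.

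The reference to 9.6.6 and 10.8 is needed. A sentence making every finding that is worse than at Visit 1 an AE would turn any worsened sign of atrophy into one, and so conflict with those sections.

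The cost is one sentence in the protocol, two short edits in the SAP and a note to sites. Listing L16.2.8.4 already shows Visit 1 beside Visit 3, so the comparison needs no new data or procedure.

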9.6.6 Rating of Symptoms

At Visits 1, 2 and 3 the blinded clinical staff or Investigator will question the patient regarding the severity of their atrophic vaginitis symptoms (see Appendix B for rating scales). The following symptoms will be evaluated:

- Vaginal Dryness
- Vaginal/Vulvar irritation/itching
- Dysuria
- Vaginal Pain associated with Sexual Activity
- Vaginal Bleeding

The severity of each symptom will be recorded on the source documents. The patients will be asked to identify which symptom is considered to be the most bothersome symptom at each visit.

CONFIDENTIAL PROTOCOL

A Randomized, Double-Blind, Placebo-Controlled, Parallel Design, Multiple-Site Study to Evaluate the Therapeutic Equivalence of Estradiol Vaginal Cream USP, 0.01% (Teva Pharmaceuticals, USA) to Estrace[®] Estradiol Vaginal Cream, USP, 0.01% (Warner Chilcott) in the Treatment of Atrophic Vaginitis

The worsening in severity of the signs and symptoms need not be additionally included as an adverse event, unless the patient requires additional treatment or the condition is an AE in the opinion of the Investigator.

9.6.7 Concomitant Medication Use

All concomitant medication use within 6 months of Visit 1 and throughout the study will be recorded.

9.6.8 Laboratory Evaluations

All patients will have a blood sample taken for evaluation of serum FSH levels. Serum FSH will be evaluated by a central clinical laboratory. Patients must have a Serum FSH > 40mIU/ml to be eligible for participation in the study.

All patients will have a blood sample taken for fasting triglyceride testing. These samples will be sent to the central laboratory for testing. Patients with fasting triglyceride values > 350 mg/dL will not be eligible for inclusion in the study.

9.6.9 Vaginal Cytology, pH Testing and PAP smear

At Visits 1 and 3, a vaginal cytology specimen will be collected by scraping the right and left lateral vaginal walls (mid-way between the fornix and introitus) with a spatula. The cells and mucus will be mixed and fixed according to the instructions provided by the central laboratory. Samples will be sent to the central laboratory for cytology testing.

The central laboratory will report the cytology results to the Investigative site before randomization. To protect the study blind, the central laboratory will not release the results of any other cytology tests other than the screening results to either the Investigator or [REDACTED] until the study is completed.

The patient's vaginal pH will be measured by inserting standardized pH paper into the vagina and comparing the color change result to the manufacturer's color chart. All Investigators will use the same type of provided pH paper (e.g., pHEM-ALERT, Gynex Corporation). pH paper should be able to read at a minimum 0.5 unit of pH changes.

At Visit 1 Patients will have a PAP smear completed during the pelvic exam if the Investigator does not have results from a PAP smear completed within the last 12 months. PAP smear samples will be sent to the central laboratory (ACM Medical Lab., Inc.) for testing.

9.6.10 Dosing Instructions and Diary

Patients will be given a dosing diary with instructions on dosage administration and diary completion. Patients will be asked to record the time and date of each dose, AEs, and concomitant medications throughout the study. The diary will be reviewed by the study staff at Visit 3/end of the study.

CONFIDENTIAL PROTOCOL

A Randomized, Double-Blind, Placebo-Controlled, Parallel Design, Multiple-Site Study to Evaluate the Therapeutic Equivalence of Estradiol Vaginal Cream USP, 0.01% (Teva Pharmaceuticals, USA) to Estrace[®] Estradiol Vaginal Cream, USP, 0.01% (Warner Chilcott) in the Treatment of Atrophic Vaginitis

9.6.11 Dosing Compliance

Dosing compliance will be checked by site staff at Visit 3 by reviewing patient diary entries. Patients will be considered compliant with dosing if they administer 75% (i.e. 6 doses)-125% (i.e., 8 doses) of the required number of doses, and do not miss more than 1 dose.

9.6.12 Dispensing Study Drug

An Independent Dispenser will dispense randomized study medication at Visit 2 with dosing instructions. The Independent Dispenser will ensure the study medication logs are reported correctly.

9.6.13 Collecting Study Drug

Study medication tubes will be collected at Visit 3 by the Independent Dispenser .

9.7 Adverse Events

The patients will be monitored throughout the study for any adverse experiences. AEs will be collected through both solicited and unsolicited means and subsequently coded in tabular form using the MedDRA Version 17.0 or higher adverse event dictionary. The patients will be encouraged to report signs, symptoms, and any changes in health to the clinic staff. Severity of each AE will be determined by the clinic staff based on observation and questioning of the patient. The Investigator will judge the relationship of the event to the study treatments.

Definitions

An adverse event is any untoward medical occurrence in a clinical investigational patient administered a pharmaceutical product, regardless of whether it has a causal relationship with this treatment. In this study, any adverse event occurring after the patient has signed the informed consent form should be recorded and reported as an adverse event.

An adverse event can, therefore, be any unfavorable and unintended physical sign, symptom, or laboratory parameter that develops or worsens in severity during the course of the study, or significant worsening of the disease under study or of any concurrent disease, whether or not considered related to the study drug. A new condition or the worsening of a pre-existing condition will be considered an adverse event. Stable chronic conditions (such as arthritis) that are present before study entry and do not worsen during the study will not be considered adverse events.

Abnormal results of diagnostic procedures, including laboratory findings, are considered to be AEs if the abnormality:

- results in study withdrawal
- is associated with a serious adverse event (SAE)
- is associated with clinical signs or symptoms
- is considered by the physician to be of clinical significance

CONFIDENTIAL PROTOCOL

A Randomized, Double-Blind, Placebo-Controlled, Parallel Design, Multiple-Site Study to Evaluate the Therapeutic Equivalence of Estradiol Vaginal Cream USP, 0.01% (Teva Pharmaceuticals, USA) to Estrace® Estradiol Vaginal Cream, USP, 0.01% (Warner Chilcott) in the Treatment of Atrophic Vaginitis

This includes events not seen at baseline, or worsened if present at baseline.

Recording and Reporting Adverse Events

For adverse event recording, the study period is defined for each patient as that time period from signature of the informed consent form through the follow-up period. For this study, the follow-up period is defined as 30 days after the last study visit.

All adverse events that occur during the defined study period must be recorded on the source documentation and transcribed onto the CRF, regardless of the severity of the event or judged relationship to the study drug. For serious adverse events, the Serious Adverse Event Form must also be completed and the serious adverse event must be reported immediately (see Section 9.8.2.). The investigator does not need to actively monitor patients for adverse events once the study has ended.

At each contact with the patient, the investigator or designee must query the patient for adverse events by asking an open-ended question. All reported or observed signs and symptoms will be recorded individually, except when considered manifestations of a medical condition or disease state. A precise diagnosis will be recorded whenever possible. When such a diagnosis is made, all related signs, symptoms, and any test findings will be recorded collectively as a single diagnosis on the CRF and, if it is a serious adverse event, on the Serious Adverse Event Form.

The clinical course of each adverse event will be monitored at suitable intervals until resolved or stabilized or returned to baseline, or until the patient is referred to the care of a health care professional, or until a determination of a cause unrelated to the study drug or study procedure is made.

The onset and end dates, duration (in case of adverse event duration of less than 24 hours), action taken regarding study drug, treatment administered, and outcome for each adverse event must be recorded on the source documentation and transcribed onto the CRF.

The relationship of each adverse event to study drug treatment and study procedures, and the severity and seriousness of each adverse event, as judged by the investigator, must be recorded as described below.

Severity of an Adverse Event

The severity of each adverse event must be recorded as 1 of the choices on the following scale:

Mild: No limitation of usual activities

Moderate: Some limitation of usual activities

Severe: Inability to carry out usual activities

CONFIDENTIAL PROTOCOL

A Randomized, Double-Blind, Placebo-Controlled, Parallel Design, Multiple-Site Study to Evaluate the Therapeutic Equivalence of Estradiol Vaginal Cream USP, 0.01% (Teva Pharmaceuticals, USA) to Estrace® Estradiol Vaginal Cream, USP, 0.01% (Warner Chilcott) in the Treatment of Atrophic Vaginitis

Causality Assessment of Adverse Events

The relationship to the study treatment is characterized as:

TERM	DEFINITION	CLARIFICATION
No Reasonable Possibility (not related)	This category applies to those adverse events which, after careful consideration, are clearly due to extraneous causes (disease, environment, etc.) or to those adverse events for which, after careful medical consideration at the time they are evaluated, are judged to be unrelated to the test drug.	An adverse experience may be considered No Reasonable Possibility if it is clearly due to extraneous causes or when (must have two): 
▪ It does not follow a reasonable temporal sequence from the administration of the IMP.▪ It could readily have been produced by the subject's clinical state, environmental or toxic factors, or other modes of therapy administered to the subject.▪ It does not follow a known pattern of response to the test drug.▪ It does not reappear or worsen when the drug is re-administered.
Reasonable Possibility (related)	This category applies to those adverse events which, after careful medical consideration at the time they are evaluated, are felt with a high degree of certainty to be related to the IMP.	An adverse experience may be considered a reasonable possibility of being related if or when (at least three of the following): 
▪ It follows a reasonable temporal sequence from administration of the IMP.▪ It could not be reasonably explained by the known characteristics of the subject's clinical state, environmental or toxic factors or other modes of therapy administered to the subject.▪ It disappears or decreases on cessation or reduction in dose. There are important exceptions when an adverse event does not disappear upon discontinuation of the drug, yet drug-relatedness clearly exists.• It follows a known pattern of response to the IMP.

